1 INTRODUCTION

1.1 Background

Abnormal epigenetic silencing of important regulatory genes has been described in various cancers, including myelodysplastic syndrome (MDS) and acute myeloid leukemia (AML) (Jones 2007). The reduction of acetylation status of histones is one mechanism for this silencing. Histone deacetylases (HDACs) are enzymes involved in the remodeling of chromatin, and therefore, have a key role in the epigenetic regulation of gene expression. Inhibitors of HDACs have been extensively studied in both hematologic and solid tumors. Four HDAC inhibitors have been approved to date by the US Food and Drug Administration (FDA) for the treatment of T-cell lymphoma, peripheral T-cell lymphoma, and multiple myeloma.

1.2 Pracinostat

Pracinostat is a rationally-designed, potent, oral, pan-HDAC (including Class I, II, and IV isoforms) inhibitor with pharmacokinetic (PK) properties allowing every other day dosing. The half-maximal inhibitory concentration (IC_{50}), across a broad range of human cancers in *in vitro* cytotoxicity assays, ranged from 0.1 to 1.5 μ M, with the lowest values noted in leukemia and lymphoma cell lines. Synergistic interactions have been observed with multiple cytotoxic and targeted anti-cancer therapeutics; notably the combination index with azacitidine ranged from 0.44 to 0.55.

1.3 Preclinical Pharmacology

Results from pharmacology studies showed that pracinostat inhibits predominantly Class I and II HDACs (inhibitory constant $[Ki] = 16$ to 240 nM). It effectively inhibits acetylation of histones and various other target proteins in a variety of human tumor cell lines at the same concentrations as it inhibits proliferation and promotes apoptosis ($IC_{50} = 0.1$ to 1.5 μ M). Lymphomas and tumors of hematological origin show the highest sensitivity.

The antitumor activity of orally administered pracinostat has been demonstrated in several xenograft mouse models of solid and hematological malignancies including colorectal cancer, ovarian cancer, prostate cancer, AML, and B cell lymphoma. As observed in the *in vitro* cell studies, hematological malignancies are most sensitive to the anti-tumor effects of pracinostat.

1.4 Clinical Experience

Pracinostat has been evaluated, either as a single agent or in combination with hypomethylating agents (HMAs), in over 430 patients with solid tumors and hematologic malignancies in multiple Phase 1 and Phase 2 clinical studies. In the initial studies, pracinostat was administered as a single agent and was found to be generally well-tolerated at doses up to 60 mg given 3 days each week (e.g., Monday, Wednesday, Friday) for 3 weeks on an every-4-week schedule. The most common manageable side effects often associated with drugs of this class, including pracinostat, are fatigue, gastrointestinal (GI) effects (nausea, vomiting, diarrhea), and myelosuppression. Please see the Investigator's Brochure (IB) for further information on

clinical studies conducted to date, adverse events (AEs) associated with pracinostat, and efficacy results.

Single-agent pracinostat has demonstrated modest activity in patients with advanced hematologic disorders. In a Phase 1 dose escalation study in 44 patients with various hematologic malignancies, pracinostat was evaluated at doses ranging from 20 to 120 mg administered orally every other day 3 times a week for 3 consecutive weeks, in a 4-week cycle. The maximum tolerated dose (MTD) was declared as 120 mg; due to dose reduction after multiple cycles of treatment, the recommended Phase 2 dose was determined to be 100 mg ([Abaza 2017](#)). Of 25 patients with AML enrolled in the study, one achieved a complete response/remission (CR) lasting 206 days, one achieved a partial response (PR) lasting 362 days, and four achieved stable disease (SD) for > 2 cycles. Three of 14 patients with intermediate or high-risk MDS achieved SD for 72 to 134 days.

A Phase 2 clinical study of oral pracinostat (60 mg every other day for 3 weeks per month) showed activity in 22 heavily pre-treated subjects with intermediate or high-risk myelofibrosis. Eight (36%) subjects experienced clinical benefit, with 6 (27%) experiencing reductions in splenomegaly (median 3 cm, range 1–4 cm) ([Quintás-Cardama 2012a](#)).

Because synergistic epigenetic effects were shown between HDAC inhibitors and HMAs, all subsequent studies have evaluated pracinostat in combination with the HMAs azacitidine and decitabine in myeloid malignancies AML, MDS, and myelofibrosis. Information on the evaluation of pracinostat in combination with HMAs in MDS is summarized in Section 1.5.

An open-label Phase 2 study evaluated pracinostat plus azacitidine in 50 patients ≥ 65 years of age with previously untreated AML and unfit to receive intensive induction chemotherapy (Study MEI-004). Pracinostat was administered orally at 60 mg every other day, 3 days a week for 3 weeks of each 4-week cycle in combination with azacitidine 75 mg/m² for 7 days of each cycle ([Garcia-Manero 2017](#)). The median age was 75 years (range 66 – 84 years); the Eastern Cooperative Oncology Group (ECOG) performance status was 0 – 1 in 84% and 2 in 16%; 66% had de novo AML and 34% had secondary AML; and the median bone marrow blasts was 40% (range 20 – 89%). The median number of treatment cycles was 6.5 (range 1 – 24+). Non-hematologic AEs grade ≥ 3 reported in > 5% of patients were fatigue 34%; anorexia 10%, cellulitis, pneumonia, asthenia, and sepsis in 8%; and urinary tract infection, nausea, back pain, hypoxia, hyponatremia, and syncope in 6%. The 30-day and 60-day mortality rates were 2% and 10%. Complete response was achieved in 21 patients (42%) and a CR with incomplete blood recovery (CRI) in 2 (4%). With a median follow-up of 21 months, the median overall survival (OS) was 19.1 months (95% confidence interval [CI], 10.0 – 26.52), and the 1-year and 2-year OS were 62% and 45%, respectively. These results compare favorably to historical data with single agent azacitidine in comparable populations and serve as the basis for conducting a Phase 3 study in patients with untreated AML unfit to receive intensive induction chemotherapy.

1.5 Rationale for the Study

Higher risk MDS in the Revised International Prognostic Scoring System (IPSS-R) classification is a serious medical condition, with a median survival of only 0.8 years in very high-risk disease and 1.6 years in high-risk disease. The only curative therapy is allogeneic stem cell

transplantation (SCT), however the vast majority of patients with MDS are not candidates for SCT given their typically advanced age, comorbidities, and lack of a suitable donor. Standard therapy with HMAs in intermediate-2 or high-risk MDS provides modest responses, though azacitidine has been shown to improve survival when compared to conventional care regimens ([Fenaux 2009](#)). Patients who do not respond to HMAs or progress after a response to HMAs have a very poor outcome, with median survival of less than one year ([Prebet 2011](#)).

Approaches to improving the treatment effect of hypomethylating therapy are clearly indicated.

A pilot Phase 2 clinical study of pracinostat in combination with azacitidine was conducted in 10 subjects with advanced MDS and showed a CR + CRI rate of 78% and a cytogenetic complete response/remission of 56% ([Abaza 2017](#)). In this study, pracinostat was administered at 60 mg, on 3 alternate days each week for 3 consecutive weeks in combination with azacitidine (75 mg/m² intravenously [IV] or subcutaneously [SC] daily × 7 days). Pracinostat dose was reduced or treatment interrupted as clinically indicated to improve tolerability and maintain patients on therapy.

These positive findings led to the conduct of a placebo-controlled Phase 2 study (MEI-003) in 102 subjects with higher-risk MDS administered pracinostat (60 mg, 3 alternate days each week for 3 weeks) or placebo in combination with azacitidine (75 mg/m² for 7 days) in 28-day cycles ([Garcia-Manero 2017](#)). The median age was 69 years (range 26–90 years), 67% of subjects had IPSS intermediate-2 risk MDS and 33% had high-risk MDS. The rate of CR by Cycle 6, the study's primary endpoint, was 18% (9/51) in the pracinostat group compared to 33% (17/51) in the placebo group ($p = 0.07$). The cytogenetic response rate in the pracinostat group was 42% (14/33) compared to 55% (17/31) in the placebo group ($p = 0.14$). Hematologic improvement was 35% (15/43) and 55% (24/44) in the pracinostat and placebo groups, respectively ($p = 0.51$). Median duration of response (DoR) was 12 months and 9 months in the pracinostat and placebo groups, respectively (hazard ratio [HR] = 0.64, 95% CI 0.23 – 1.79). With a median duration of follow-up of 15 months, the median OS in the pracinostat and placebo group was 16 and 19 months, respectively (HR = 1.21, 95% CI, 0.65 – 2.23). The median event-free survival (EFS) was 9 months in both groups (HR = 0.82, 95% CI 0.46 – 1.46) and the 1-year OS was 60% in both groups.

In that study, 26% of subjects in the pracinostat group discontinued study drugs in the first 3 cycles of therapy (by Day 84) for reasons other than progressive disease (PD) or SCT as compared to 10% of subjects randomized to the placebo group. The most common cause for early discontinuations in the pracinostat group was AEs; primarily fatigue and myelosuppression. Furthermore, in the intermediate-2 risk group, 14/30 subjects (47%) randomized to pracinostat discontinued the study due to AEs or withdrawal of consent at any time in the study compared to 4/33 subjects (12%) randomized to placebo, whereas in the high-risk group, the discontinuation rate due to adverse events/withdrawal was comparable in the 2 treatment arms; 27% in pracinostat versus 22% in placebo.

In a post-hoc analysis, the subset of subjects who received at least 4 cycles of pracinostat + azacitidine and began Cycle 5 had a trend for better progression-free survival (PFS) and OS (HR = 0.67) compared to the control group. This suggests the lack of efficacy in the intent-to-treat (ITT) population may be due to early discontinuations and insufficient exposure to pracinostat. This is further supported by the data from Study MEI-004 in elderly AML where

the discontinuation rate was lower (8% in the first 2 cycles) resulting in substantial treatment efficacy, with a CR rate of 42% and a median survival of 19.1 months ([Garcia-Manero 2016](#)). Therefore, this current study will evaluate a regimen consisting of a lower dose of pracinostat in combination with the standard dose of azacitidine to determine if the rate of early discontinuation can be reduced, thereby improving efficacy.

1.6 Rationale for Pracinostat Dose Selection

This study will investigate a pracinostat dose of 45 mg, 25% lower than the dose used in Study MEI-003. The rationale for selecting a pracinostat daily dose of 45 mg for this regimen include:

- The dose of 45 mg has been used in prior Phase 2 studies in MDS and AML as the step-down dose level for subjects who did not tolerate the starting dose of 60 mg.
- In prior studies in MDS and AML, approximately 50% of subjects who achieved an objective response and received pracinostat for more than one year had their daily dose reduced from 60 mg to 45 mg, indicating this dose is efficacious and well tolerated.
- A dose of 40 mg was shown to induce a 2-fold increase in histone 3 acetylation (acH3) in 17 subjects with solid tumors, a level comparable to that achieved with a dose \geq 60 mg but significantly higher than achieved with a dose of 20 mg, suggesting that a dose of 45 mg may be sufficient for full pharmacodynamic effects.
- A dose of 45 mg results in plasma concentrations greater than HDAC C1 K_i for approximately 24 hours, suggesting adequate HDAC inhibition at this dose (data on file).

1.7 Rationale for Patient Population

The study will enroll only patients with high and very high-risk MDS by IPSS-R because this is a patient subset with the shortest overall survival and the most significant unmet need. Furthermore, in Study MEI-003, patients with high-risk MDS randomized to pracinostat plus azacitidine had a discontinuation rate similar to that observed with azacitidine plus placebo, whereas patients with intermediate-2 MDS had a higher discontinuation rate in the pracinostat + azacitidine group, suggesting a different level of tolerability to treatment toxicities.

2 STUDY OBJECTIVES

2.1 Primary Objectives

The primary objectives of this study are to:

- Define the safety and tolerability of pracinostat plus azacitidine in high/very high-risk MDS
- Determine the overall response rate (ORR), defined as complete remission (CR) and partial remission (PR), of pracinostat plus azacitidine in high/very high-risk MDS

2.2 Secondary Objectives

Evaluate the following endpoints in patients with high/very high-risk MDS administered pracinostat plus azacitidine:

- CR rate
- Overall hematologic improvement (HI) rate
- Clinical benefit rate, defined as rate of CR + PR + HI + Marrow CR
- Rate of cytogenetic CR
- DoR
- Rate of leukemic transformation
- EFS
- PFS
- OS

3 STUDY DESIGN

This is a Phase 2, two-stage study of the safety and efficacy of pracinostat in combination with azacitidine in patients with IPSS-R high and very high-risk MDS who are previously untreated with HMAs. Enrollment in this study will be limited to high/very high-risk MDS because this group represents the highest unmet need, with median survival of less than 18 months.

Recognizing that additional safety and efficacy of pracinostat plus azacitidine is desirable before evaluating the treatment regimen in a placebo-controlled environment, the protocol is being amended to become a 2-stage open-label study comprising Stage 1 and Stage 1 expansion (Stage 1b).

Stage 1 will be conducted as an open-label single arm in approximately 40 evaluable subjects to assess if the pracinostat dose regimen results in a discontinuation rate that meets a predefined threshold, and the observed efficacy justifies expansion of enrollment in Stage 1b.

A discontinuation rate of approximately $\leq 10\%$ in Stage 1, a rate comparable to that observed with azacitidine alone in Study MEI-003, would support expansion to Stage 1b. Stage 1b will be conducted as an open-label arm to achieve a total enrollment of approximately 60 subjects evaluable for efficacy, inclusive of Stage 1 and Stage 1b enrollment.

Study drugs should be continued until disease progression or intolerable toxicity. It is important to note that the median time to achieving a response with azacitidine alone is 4 to 5 months. Therefore, early (< 6 months) discontinuation of study therapy for ‘no response’ should be avoided. The Medical Monitor should be contacted by the Investigator prior to discontinuing study drugs in a subject from the study to discuss the rationale for discontinuation.

After discontinuing study drugs, subjects will be followed every 3 months (± 1 month) until death or study termination to collect information on disease status (i.e., improvement of disease

response or disease progression), start of non-protocol therapies (e.g., stem cell transplant or an MDS-directed therapy) and survival.

The primary study analysis will be performed approximately 12 months after the last subject is enrolled in the study. The study duration is anticipated to be approximately 36 months: 24 months for enrollment and 12 months of follow-up until the primary analysis. At the completion of the primary analysis, the Sponsor will decide whether to terminate the study or continue study drug dosing in ongoing subjects.

It is anticipated that subject participation in the study will be for a median of approximately 10 cycles in the group receiving pracinostat + azacitidine.

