Classical cytogenetics shall be required on BMBx and aspiration at screening, and subsequent assessments as indicated. Cytogenetics are performed as standard of care to classify the subject's MDS in the corresponding IPSS-R risk category and to determine cytogenetic remission/response.

Fluorescence in situ hybridization (FISH) and molecular tests (e.g., polymerase chain reaction) may be conducted as per institutional standard of care but are not required. If performed, the results should be documented in the case report form (CRF).

STATISTICAL METHODOLOGY

Sample Size

Approximately 60 subjects evaluable for efficacy will be enrolled, including approximately 40 evaluable subjects in Stage 1 and the remaining subjects in Stage 1b. Non-evaluable subjects will be replaced.

Sample size calculation for Stage 1

The goal of Stage 1 is to establish a pracinostat/azacitidine regimen with a discontinuation rate of approximately up to 10% in the first 3 cycles of therapy, a rate comparable to that observed in the azacitidine/placebo group in study MEI-003. The 95% confidence interval (CI) approach is utilized to estimate the sample size in Stage 1. The number of subjects to be enrolled is calculated such that the lower bound of the 95% CI of the discontinuation rate will be no more than 12% below the point estimate of 22.5%, the mid-point between the discontinuation rates in the azacitidine/placebo (10%) and azacitidine/pracinostat (32%) groups, respectively, in study MEI-003.

With a sample size of 40 subjects, the study will be stopped if ≥ 9 subjects (22.5%, 95% CI: 10.8% – 38.4%) discontinue in the first 3 cycles. Under this scenario, the lower bound of the 95% CI is > 10 % (above the pre-specified desired goal) and the upper bound of the 95% CI is > 32 % (higher than the discontinuation rate in study MEI-003).

It is also possible to conclude that the desired threshold of a discontinuation rate of ≤ 10 % has been achieved with fewer than 40 subjects treated in Stage 1. For example, if 4 discontinuations are observed in the first 32 subjects, the lower and upper bounds of the 95% CI around the observed discontinuation rate of 12.5% (4 of 32) are 3.5% and 29.0%, lower than reported with azacitidine/placebo and azacitidine/pracinostat, respectively, in study MEI-003. This would justify expanding enrollment in Stage 1b of the study after only 32 subjects have been treated for ≥ 3 cycles.

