9 STATISTICAL PLAN

9.1 Sample Size

Approximately 60 subjects evaluable for efficacy will be enrolled: approximately 40 in Stage 1 and 20 in Stage 1b. Non-evaluable subjects will be replaced.

9.1.1 *Sample Size Calculation for Stage 1*

The goal of Stage 1 is to establish if this pracinostat + azacitidine regimen achieves a discontinuation rate of approximately $\leq 10\%$ in the first 3 cycles of therapy, a rate comparable to that achieved in the azacitidine + placebo group in Study MEI-003. The 95% CI approach is utilized to estimate the sample size in Stage 1. The number of subjects to be enrolled is calculated such that the lower bound of the 95% CI of the discontinuation rate will be no more than 12% lower than the point estimate of 22.5%, the midpoint between the discontinuation rates in the azacitidine + placebo (10%) and azacitidine + pracinostat (32%) groups, respectively, in Study MEI-003.

With a sample size of 40 subjects, the study will be stopped if ≥ 9 subjects (22.5%, 95% CI: 10.8–38.4%) discontinue in the first 3 cycles. Under this scenario, the lower bound of the 95% CI is > 10 % (above the pre-specified desired goal) and the upper bound of the 95% CI is > 32 % (higher than the discontinuation rate in study MEI-003).

It is also possible to conclude that the desired threshold of a discontinuation rate of ≤ 10 % has been achieved with fewer than 40 subjects treated in Stage 1. For example, if 4 discontinuations are observed in the first 32 subjects, the lower and upper bounds of the 95% CI around the observed discontinuation rate of 12.5% (4 of 32) are 3.5% and 29.0%, lower than reported with azacitidine/placebo and azacitidine/pracinostat, respectively, in Study MEI-003. This would justify expanding enrollment to Stage 1b of the study after only 32 subjects have been treated for ≥ 3 cycles.

In addition to the discontinuation threshold, an observed ORR of ≥ 20 % will be desired to support opening Stage 1b of the study because it is expected that azacitidine alone results in an ORR of approximately 20% in high/very high-risk MDS.

The study's Independent Data Monitoring Committee (IDMC), in coordination with the Sponsor, will determine when enrollment in Stage 1 can be concluded, and whether to open enrollment in Stage 1b.

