9.2 Analysis Populations

The primary efficacy analysis will be conducted using the ITT population, which is defined as all treated subjects. Exploratory analyses will be performed for the Per-Protocol population, defined as subjects who received at least 2 cycles of therapy and a follow-up bone marrow assessment.

The Safety population, defined as all subjects who have been treated, will be used for the safety analysis.

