9.3.2 Safety Analysis Endpoints

Safety endpoints will include the incidence of treatment-emergent AEs (TEAEs), characterized and graded using NCI CTCAE v4.03, and changes in laboratory results, ECG findings, physical examinations, vital signs, and ECOG performance status.

Safety will be assessed through the analysis of the reported incidence of TEAEs, including SAEs, dose-limiting toxicities, AEs leading to withdrawal, events of at least CTCAE Version 4.03 Grade 3 in severity, and AEs related to study drug. Treatment-emergent AEs are those with an onset on or after the initiation of therapy. Other safety endpoints include laboratory results, ECG findings, physical examinations, vital signs, and changes in ECOG performance status. A copy of CTCAE Version 4.03 scoring system may be downloaded from:
http://evs.nci.nih.gov/ftp1/CTCAE/CTCAE_4.03_2010-06-14_QuickReference_8.5x11.pdf.

Adverse events will be summarized by Medical Dictionary for Regulatory Activities (MedDRA) coding terms, system organ class, and preferred term for all subjects in the Safety population. The AEs will also be tabulated by maximum severity and relationship to study drug where applicable. Other safety endpoints, including laboratory results, vital signs, and shifts in ECG findings, will be summarized for all subjects in the Safety population. AESIs will be presented also in specific summary table(s) and listing(s).

Concomitant medications will be coded using the WHO-Drug Dictionary and they will be listed and summarized.

The rate of discontinuation, defined as the number of subjects who discontinue study drugs prior to study completion divided by the number of subjects treated, will be calculated for all subjects and for subjects who complete Cycle 3 and Cycle 6.

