3 STUDY DESIGN

3.1 Overall Study Design

This study is a two stage Phase 2 trial in subjects with IPSS-R high and very high risk myelodysplastic syndromes (MDS) previously untreated with hypomethylating agents.

Stage 1 is an open-label portion in approximately 40 evaluable subjects will be treated with pracinostat and azacitidine. The goal of Stage 1 is to evaluate treatment tolerability – based on whether the combination regimen of pracinostat and azacitidine’s rate of treatment discontinuation due to possibly safety reasons in the first 3 cycles of therapy is not significantly higher than 10%, and to determine if the observed efficacy justifies expansion of enrollment in Stage 1b based on ORR.

Stage 1b is an open-label expansion to achieve a total enrollment of approximately 60 subjects evaluable for efficacy, inclusive of Stage 1 and Stage 1b enrollment.

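### Is the Stage 1 discontinuation rule read only on evaluable subjects, so that early stops drop out of the count?

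*Protocol*

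**What the plan says.** Protocol section 3 says Stage 1 is conducted "in approximately 40 evaluable subjects to assess if the pracinostat dose regimen results in a discontinuation rate that meets a predefined threshold"; the same sentence adds a second purpose, judging whether observed efficacy justifies expansion. SAP 3.1 has similar wording: "Stage 1 is an open-label portion in approximately 40 evaluable subjects will be treated with pracinostat and azacitidine". The Protocol synopsis makes these 40 part of the response sample: "Approximately 60 subjects evaluable for efficacy will be enrolled, including approximately 40 evaluable subjects in Stage 1". Protocol 9.1 and SAP 4 then add the replacement rule: "Non-evaluable subjects will be replaced".

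Other text points to treated subjects. Protocol 9.1.1 allows a conclusion with "fewer than 40 subjects treated in Stage 1", and Protocol 9.3.2 defines a discontinuation rate as those who "discontinue study drugs prior to study completion divided by the number of subjects treated". The stop rule in Protocol 9.1.1 and SAP 4.1 is 9 or more of 40 subjects, with no adjective. The early-expansion example (4 stops in 32) would open "Stage 1b of the study after only 32 subjects have been treated for ≥ 3 cycles".

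Evaluability for efficacy is defined in Protocol 9.2, under the name Per-Protocol, as "subjects who received at least 2 cycles of therapy and a follow-up bone marrow assessment". SAP 13 renames that set Efficacy Evaluable. SAP 5.3 adds subjects who progress before completing 2 cycles and ties the set to endpoints that need marrow or blood assessments.

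**The concern.** Tolerability over the first three cycles is a main Stage 1 question, and the discontinuation rate feeds the decision to stop or expand. Protocol section 3 puts the word evaluable beside that rate, and no sentence names the population for the gate or says whether a replaced subject still counts in 9 of 40 or 4 of 32.

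If the efficacy definition were carried over to the gate, a subject who stopped for toxicity or withdrew consent before 2 cycles would leave both numerator and denominator and be replaced by someone else. The observed rate would be biased downward. It would also no longer be comparable with the 26% and 10% from Study MEI-003 (Protocol 1.5), which are percentages of all subjects in each group. A poorly tolerated regimen could then pass the gate.

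**Working it through.** **1. The plan's own figures.** Exact (Clopper-Pearson) 95% limits:

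- 9/40 = 22.5%: 10.84% to 38.45% (stated 10.8% to 38.4%).
- 8/40 = 20.0%: lower limit 9.05%, so 9 is the smallest count of 40 with a lower limit above 10%.
- 4/32 = 12.5%: 3.51% to 28.99% (stated 3.5% and 29.0%).

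The arithmetic is right for any 40 or 32 subjects. The only question is who they are.

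**2. Size under the unfavourable reading.** Let p be the true 3-cycle rate among treated subjects, and s the share of those stops that occur before the subject becomes evaluable. With replacement, the rate among evaluable subjects is

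q = p(1 − s) / (1 − ps),

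and 40/(1 − ps) subjects must be treated to obtain 40 evaluable. The inputs are p = 26% (Protocol 1.5) and p = 32% (Protocol 9.1.1). The documents do not give s, so a range is assumed. For example, with p = 0.26 and s = 1/2, q = 0.13/0.87 = 14.9% and 40/0.87 = 46.0 are treated.

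| s (assumed) | q, p = 26% | Treated for 40 evaluable, p = 26% | P(≥ 9 of 40), p = 26% | P(≤ 4 of 32), p = 26% | P(≥ 9 of 40), p = 32% |
|---|---|---|---|---|---|
| 0 | 26.0% | 40.0 | 74.8% | 5.5% | 93.2% |
| 1/6 | 22.6% | 41.8 | 57.0% | 11.9% | 83.5% |
| 1/4 | 20.9% | 42.8 | 46.0% | 17.3% | 75.2% |
| 1/3 | 19.0% | 43.8 | 34.4% | 24.7% | 64.1% |
| 1/2 | 14.9% | 46.0 | 13.3% | 46.8% | 34.8% |

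Under that reading the effect would be large.

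**3. Does the plan support that reading?**

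- *Event rule.* SAP 2.3.2 and 9.2 count every reason for stopping in the first three cycles, other than progression and transplant, as an event, for both stages. Dropping toxicity stops before 2 cycles would contradict this.
- *Stage 1 decision.* SAP 11.2 assesses Stage 1 on the discontinuation rate for possibly safety-related reasons, which is the same endpoint. It most naturally inherits that endpoint's definition.
- *Default population.* SAP 9 defaults to ITT and SAP 10 to Safety. SAP 5.2 makes the two identical: everyone who received a dose. SAP 15 plans a discontinuation table by stage.
- *Scope of evaluable.* SAP 5.3 restricts the set to marrow and blood endpoints and to supportive efficacy analyses. Discontinuation is neither.
- *Replacement.* In Protocol 9.1 and SAP 4 the replacement sentence directly follows the efficacy enrolment target, so it reads as part of that target.
- *The 4-of-32 example.* The four who stopped are kept within the 32. The phrase about treatment for at least 3 cycles cannot literally describe them; it loosely means that the window has elapsed.

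**4. Size under the treated reading.** On the first 40 or 32 treated subjects, the stated intervals hold as printed. If replacement takes Stage 1 past 40 and all treated subjects are counted, 9 events keep the lower limit above 10% up to 43 treated (9/43: 10.04%; 9/44: 9.80%), and a tenth event restores it even at 48 (10/48: 10.47%). Expected events also rise with the number treated: 0.26 × 40 = 10.4 against 0.26 × 46 = 12.0. Nothing is hidden by replacement.

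**The case for a change.** The strongest case for a change is that Protocol section 3 attaches evaluable to the discontinuation assessment itself. The SAP defaults settle the final table but are not stated for the Stage 1 decision. The rate in Protocol 9.3.2 covers any stop before study completion, so it does not strictly govern the 3-cycle gate. The early stops at risk are also the ones that matter: Protocol 1.5 reports that adverse events were the most common cause of early discontinuation in the MEI-003 pracinostat group. One clarifying sentence would cost nothing.

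What stands is that no sentence names the gate population or says what happens to replaced subjects, and that the 32-subject phrase is careless.

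What does not stand is the step from loose wording to a biased rule. The sentence in Protocol section 3 covers two purposes, tolerability and efficacy, and evaluable fits the second. To reach the bias, an analyst would have to take a set that the SAP confines to marrow and blood endpoints, apply it to a discontinuation rate, and set aside the SAP's explicit event rule. The decision is also not mechanical: the figures are approximate, no formal interim analysis is planned (SAP 11.2), and the IDMC advises the Sponsor after reviewing safety data (Protocol 9.4).

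**Conclusion.** No change to the plan is needed. This is a gap in wording that analysts fill sensibly: a discontinuation rate is computed on the subjects who started treatment, and the SAP's event rule and default populations lead there. On that reading the boundary of 9 in 40 and the example of 4 in 32 reproduce, and over-enrolment for the response target has little effect.

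The fall in the chance of stopping from 75% to 46% or 13% at a true rate of 26% needs two things together: a reading that conflicts with SAP 2.3.2, 5.3 and 9.2, and an assumed share of stops before evaluability (1/4 or 1/2) that appears nowhere in the documents. It shows what a misreading would cost, not what the plan prescribes. The conclusion rests on the Stage 1 assessment using the endpoint as the SAP defines it. The IDMC charter, which may state this directly, is not among the documents.
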